10.0 Study Design / Methods

We will conduct brain stimulation with 17 randomized adolescent participants at initial enrollment. Drop-outs are expected, with the goal of having 10 youths with ASD complete the study, with the same number of parents actively participating by the end of the experiment.

The following table summarizes the schedule of activities for a subject:

Schedule of events	Activities	Time commitment for volunteer	Compensation
Initial visit with research coordinator, Drs. [name] and [name]	Consent (parent and child)	15 min	\$25 (child) \$15 (parent)
	Medical & MRI screening (parent and child)	5 min	
	ADOS-2 & KBIT-2 (with child), clinical measures (with parent)	90 min	

	Mock scanner training with child	10-15 min	
	fMRI scanning with child	30 min	
	tDCS acclimation with child	10 min	
PEERS weekly sessions	PEERS training plus active / sham tDCS	1 hr / week x 14 weeks	\$15 per session (child) \$0 (parent)
Post-intervention visit	clinical measures (with parent), fMRI scanning (with child)	45 minutes	\$25 (child) \$25 (parent)
14-week follow-up visit	clinical measures completed online (by parent)	30 minutes	\$10 (child) \$50 (parent)

Parents will make initial phone or email contact with the study coordinator. The study coordinator will conduct a brief telephone screening to determine preliminary eligibility for the study. If eligible, the study coordinator will schedule the initial visit.

The initial visit will last approximately 3 hours. Following informed consent (see Section 9.0), an in-depth MRI screening form will be filled out by the parent and the medical history information obtained during the initial telephone interview will be reconfirmed. Any female participants will complete a pregnancy test. [name] will then conduct the ADOS and K-BIT with the child while the parent completes the following clinical outcome measures on a computer (using RedCap) in a separate room: Social Responsiveness Scale-2 [26], the Social Skills Improvement System, the Quality of Play Questionnaire, the Aberrant Behavior Checklist, and the Test of Adolescent Social Skills Knowledge-Revised [27]. The child and parent are given a 10-minute break and a healthy snack, if desired.

Following the break, the child is introduced to the tDCS electrodes placed on the scalp with no stimulation as an initial step in the acclimation process. Because some individuals with ASD can be excessively sensitive to certain sensory stimuli, this initial introduction to the electrodes is important. While the subject is being acclimated to the electrodes, the research coordinator explains the fMRI task to the child and demonstrates the task on a computer. The electrodes are removed, then the child is placed in the mock scanner. The mock scanner introduces the participants to the scanning environment by laying in the bore of a simulated scanner, listening to MRI sounds, practicing button presses and playing a game that awards points for keeping head movement to a minimum (via a head tracker in the mock scanner controlling the cursor – the longer the subject keeps their head in the same location, the longer the cursor stays on a bullseye and the more points they accumulate). Participants will play the bullseye game for 5 minutes. [name] prior experience in scanning youths with ASD indicates that they can keep their heads still for this period of time. The subject will then practice the fMRI task in the mock scanner for about 3 minutes.

After mock scanner training, subjects are taken to the MRI scanner and placed on the scanner bed in a comfortable position, with blankets and head cushioning. The child is told that the parent is always nearby and that the research team will be able to talk to them through the headphones. Additional ear protection is provided in the form of foam ear plugs. When subjects are in the scanner but not performing any particular task, a movie will be played for them. The child is given a button box to hold in their dominant hand in order to make responses during the fMRI task. In the other hand is a squeeze ball that should only be used to alert the research team if they feel panicked and need to come out of the scanner. During scanning, the research coordinator and MRI technician are in frequent verbal contact with the subject and will always tell the subject what to expect in terms of noises and duration of a scan. Total scanning time is approximately 20 minutes.

Pre- and post-treatment fMRI sessions will use a task in which two visual stimuli are presented simultaneously then removed, with the location of one image replaced by a probe[28]. Participants respond with the index or middle finger of the preferred hand to indicate the probe location. In this type of probe task, brain activation is expected to be higher for probes that are in the same location as the stimulus that is attended more. Reaction time is also expected to be faster if the probe appears in a location that was just recently attended compared to the location that was not attended. In one condition, the stimuli are a face and house to assess attentional bias to faces versus non-faces (related to social awareness). Another condition presents a face with direct gaze and one with averted gaze (related to social motivation, social anxiety). These conditions are implemented in functional runs lasting 5 minutes each and each run is repeated twice. The runs are presented in counterbalanced order across subjects. Following fMRI scanning, an additional tDCS acclimation session is completed. Electrodes are placed on the scalp again, and current is gradually increased to the desired level over a 5-minute period. The child will watch a movie or play a video game during this acclimation period.

Following the baseline visit, subjects will return on a different day for the PEERS training. PEERS is a parent-assisted intervention that teaches targeted social skills to high-functioning patients with ASD during fourteen weekly sessions. Parents and adolescents attend separate concurrent sessions that instruct them on key elements about making and keeping friends.

Each adolescent PEERS session begins with a didactic section, approximately 30 minutes in duration. Then the group conducts role plays modeling the correct and incorrect ways to utilize the weekly skill set. Next, the group reviews homework from last week and then discusses homework for next week. During the last 10-15 minutes of the session, the adolescents and parents are reunified to discuss the homework assigned for next week.

Each parent session begins with a detailed review of each adolescent's progress on the previous week's homework. Then the parents are given didactic information about the weekly skills set. Finally, the parents are reunified with the adolescents in order to discuss the plan for completion of assigned homework for next week.

Topics covered during the PEERS program include the following:

1. Conversational skills, including verbal and nonverbal forms of communication;
2. Electronic forms of communication, including phone calls, text messaging, instant messaging, emailing, and online safety;
3. Developing friendship networks, including identifying relevant peer
4. Groups and extra-curricular activities in which to find sources of potential friends;
5. Appropriate use of humor, including learning to pay attention to humor feedback from others;
6. Peer entry strategies, including how to join conversations with other adolescents;
7. Peer exiting strategies, including how to assess receptiveness during peer entry and what to do when these attempts fail;
8. How to have successful get-togethers, including how to organize and execute a gathering with friends;
9. Good sportsmanship, including how to appropriately behave during games and sports;
10. Handling teasing, including distinguishing teasing from embarrassing feedback and handling verbal teasing through the use of appropriate behavioral responses;
11. Handling bullying, including identifying strategies for handling cyber bullying and physical threats from others;
12. Changing reputations, including long-term strategies for altering a bad reputation;
13. Resolving arguments with friends, including specific steps for problem solving disagreements; and handling rumors and gossip, including behavioral strategies for minimizing the damage caused by gossip.

Subjects will receive tDCS weekly in conjunction with their PEERS session. Half of the adolescent participants will be randomly assigned to receive active tDCS of the left dorsolateral prefrontal cortex (DLPFC), and half will receive sham tDCS to the same location. Active / sham assignment does not change over the course of the experiment. However, within each condition, half of the participants will receive tDCS during the first 30 minutes and half will receive tDCS during the second 30 minutes. This schedule will then be reversed at each session. This will counterbalance the time of tDCS delivery and will increase the feasibility of setting up tDCS in a reasonable time window. Sham tDCS is achieved by wiring all group participants to separate computer-controlled tDCS programs. All participants receive an initial brief dose; those receiving sham treatment are then automatically decreased to zero by the computer, allowing all clinical personnel to remain blind to the participant's condition. Participants themselves are also blind to condition as most people report that the tingling sensation associated with tDCS decreases within the first few minutes of treatment.

For participants randomized to receive active treatment, tDCS will be delivered in 30-minute sessions with the Chattanooga Ionto system using 1.5mA current. This constant current device ramps up to the desired amplitude to minimize discomfort for participants and ramps the amplitude back to 0mA at the end of the session. Electrodes will be standard small (4x4 cm) sponge electrodes soaked in a sterile solution of 0.9% sodium chloride insulated by a latex casing. The current density and total charge delivered by the above parameters is consistent with those used safely in the current research literature. In all tDCS conditions, the anode will be placed on the scalp over the area corresponding to the left DLPFC (position F3 from the EEG 10-20 system located via a commercial EEG electrode placement cap), a brain region postulated to have deficient neural inhibition in ASD [29-30] and demonstrated to be a potential tDCS site for the reduction of symptoms associated with ASD[21]. The cathode will be on the scalp over the area corresponding to the right DLPFC (position F4 from the EEG 10-20 system located via a commercial EEG electrode placement cap). Specially designed software (authored by investigator [name]) interfaces with an ONTRAK ADU218 Solid State Relay I/O interface connected to the tDCS device permitting normal and reverse current flow between the electrodes in a manner that is completely masked. The software reads the assigned condition directly from an encrypted participant-randomization-file and delivers anodal or sham stimulation in a blinded fashion.

A brief questionnaire about adverse effects will be completed with participants and their parents immediately following the second and last treatment sessions. Tolerance for tDCS will be monitored during tDCS delivery by noting the frequency with which a subject reported irritation, discomfort, burning or pain, whether a subject attempted to remove the tDCS leads, whether a subject wished to discontinue the procedures due to the tDCS (rather than the PEERS training). After the second and last PEERS sessions, the experimenters will administer a brief questionnaire with the subject about whether they felt uncomfortable itching, tingling, burning during the session or whether they have had headaches, neck pain, sleepiness, moodiness in the past week. Any of these effects will be recorded. We will conclude that tDCS can be tolerated if these effects are experienced less than 25% of the time for a given individual. We will also report on how many subjects tolerated the procedures.

The child and parent receive compensation in the form of gift cards following each visit to MUSC (see Table above).

After 14-weeks of PEERS training, subjects will return for a post-treatment session in which the clinical outcome measures will be completed by parents and fMRI session will be completed by the participants (same procedures as before excluding tDCS acclimation).

Finally, 14 weeks after the post-treatment session, the parent will be sent a reminder via RedCap to complete the clinical outcome measures. In addition, both parent and child will be asked to guess which condition the child was assigned to (active or sham tDCS). Once the final follow-up surveys are completed in RedCap, the final gift card of \$75 is mailed to the family.

Information about which condition a subject was assigned to is not typically provided, but if a subject asks, we can tell them after all study procedures are completed and the blind is lifted. Study personnel will also be asked to guess the condition before the study blind is lifted.

Source records: the data collected from subjects include: parental and subject responses on clinical tests and questionnaires, anatomical and functional MRI scans, reaction time and accuracy responses on the fMRI task.

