1.0 Objectives / Specific Aims

One of the hallmark symptoms of Autism Spectrum Disorder (ASD) is difficulty with social communication and interaction. Although numerous behavioral interventions have been developed to address social difficulties in ASD, one evidence-based social skills training program in particular has demonstrated promise in improving social skills knowledge and social functioning: the UCLA Program for the Education and Enrichment of Relational Skills (PEERS)[1], which is a manualized, evidence-based program for high-functioning adolescents with ASD. Despite the success of this program, not all individuals benefit from social skills training[2]. Reasons for non-responsiveness are likely complex and varied, ranging from differences in neural responsiveness, cognitive function, temperament and social support. One neurocognitive factor that may impact social learning is the ability to filter out irrelevant information, or attend to relevant social information [3]. Therefore, targeting selective attention at the neural level may have benefits for social skills learning. Recently, brain stimulation techniques such as transcranial direct current stimulation (tDCS) and repetitive transcranial magnetic stimulation (rTMS) have shown promise in enhancing learning, attention and other behavioral outcomes in ASD [4-6].

In the present proposal adolescents with ASD who will receive PEERS training with active or sham tDCS to determine whether social skills training can be enhanced with neuromodulation. tDCS is a minimally invasive neuromodulatory technique that delivers low current through scalp electrodes. tDCS modulates ongoing neural activity by affecting neuronal membrane potential. tDCS has shown some promise in reducing neuropathic pain [7], alleviating symptoms in some psychiatric disorders [8-9] and enhancing motor function following stroke [10]. tDCS was chosen as a neuromodulatory technique in the present proposal due to its portability which is well suited to allow for tDCS to be delivered concomitantly with social skills training, which requires interaction with a group of individuals. Animal studies also suggest that the effects of tDCS stimulation may last beyond the period of stimulation [11].

The aims of this study are to:

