4.0 Study Endpoints (if applicable)

The primary endpoints are changes in responses on various clinical measures pre- and post-intervention: the Social Responsiveness Scale, the Social Skills Improvement System, the Quality of Play Questionnaire, the Aberrant Behavior Checklist, and the Test of Adolescent Social Skills Knowledge-Revised. We predict that participants receiving active tDCS will show greater improvement in these measures compared to those receiving sham tDCS. This will be assessed using non-parametric t-tests (IBM SPSS Statistics, Chicago, IL) conducted separately for each measure.

Secondary endpoints will be fMRI response and reaction time pre- and post-intervention on a laboratory test of attention and social information processing.

The primary safety endpoint will be self-reported adverse effects of tDCS collected after each treatment session.

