7.0 Setting

- The initial visit to MUSC will take place at the Center for Biomedical Imaging (CBI) at [name]. Baseline assessments using ADOS-2 and K-BIT2 and tDCS acclimation will take place in a quiet testing room in the CBI facility. Parents will fill out questionnaires in an adjacent area at CBI. These questionnaires will be entered into RedCap and no identifying information will be linked to the survey responses.
- tDCS acclimation, Mock scanner training, and fMRI scanning will also take place at CBI.
- Brain stimulation with active or sham tDCS will take place in the MUSC Institute of Psychiatry South, 5th Floor

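### As written, the parent completes the adolescent social skills knowledge test, one of five primary efficacy measures, and nothing schedules the adolescent to take it

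*Combined protocol and SAP*

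**What the plan says.** Section 4.0 states: "The primary endpoints are changes in responses on various clinical measures pre- and post-intervention". It then names five instruments, of which the knowledge test is the fifth. It adds "Secondary endpoints will be fMRI response and reaction time pre- and post-intervention" and, for safety, "The primary safety endpoint will be self-reported adverse effects of tDCS collected after each treatment session".

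Section 10.0 describes the initial visit. The child has the ADOS and K-BIT "while the parent completes the following clinical outcome measures on a computer (using RedCap) in a separate room". The list that follows ends with "the Aberrant Behavior Checklist, and the Test of Adolescent Social Skills Knowledge-Revised".

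Section 7.0 agrees: "Baseline assessments using ADOS-2 and K-BIT2 and tDCS acclimation will take place in a quiet testing room", and "Parents will fill out questionnaires in an adjacent area at CBI".

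For the two later assessments, the Section 10.0 schedule table and narrative both give the clinical measures to the parent, online in the case of the 14-week follow-up.

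**The concern.** By its name, the test concerns what adolescents know about social skills. Section 1.0 treats knowledge as an outcome in its own right, saying that PEERS has "demonstrated promise in improving social skills knowledge and social functioning". Only the adolescents are randomised to active or sham tDCS, while parents in both arms are taught the weekly skills in their own sessions. A form completed by the parent is therefore not a direct test of knowledge in the person who was stimulated.

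The documents do not say how the parent is to answer, and each possibility has a cost:

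- **From the parent's own knowledge.** The score then describes someone who received no tDCS. Stimulation could reach it only indirectly, through the adolescent.
- **As a proxy for the adolescent.** The measure then becomes a fifth parent report and not a test.

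Either way, no primary efficacy measure would come directly from the adolescent. Once PEERS teaching begins, a pre-training adolescent score cannot be obtained afterwards.

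**Working it through.** No sample size, power or error-rate figure bears on this point, so the check is a comparison of the text.

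**Step 1: count the primary efficacy measures (Section 4.0).** There are five, and the knowledge test is one of them.

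**Step 2: find the respondent at each assessment.**

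| Assessment | Schedule table (10.0) | Narrative | Tasks given to the adolescent |
|---|---|---|---|
| Initial visit | Clinical measures: parent | Parent, in a separate or adjacent room (7.0, 10.0) | ADOS-2, K-BIT2, mock scanner, fMRI, tDCS acclimation, pregnancy test if female |
| Post-intervention | Clinical measures: parent | Parent (10.0) | fMRI |
| 14 weeks | Clinical measures: parent, online | Parent, by RedCap reminder (10.0) | Guess of assigned condition |

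Between the first two assessments the adolescent has PEERS with tDCS and answers adverse-effect questions. The knowledge test appears among the adolescent's tasks nowhere.

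**Step 3: count.**
- Assessments at which the clinical measures go to the parent: 3 of 3.
- Assessments at which the adolescent is scheduled to take the knowledge test: 0 of 3.
- Primary efficacy measures completed by the parent: 5 of 5.
- Efficacy endpoints measured directly on the adolescent: fMRI response and reaction time, both secondary.

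**Step 4: look for text pointing the other way.** The source-records paragraph at the end of Section 10.0 mentions responses from subjects as well as parents, on tests and on questionnaires. It names no instrument and no visit. The adolescent's ADOS-2 and K-BIT2 can account for the tests, and the adverse-effects questionnaire for the rest. The line is compatible with an adolescent form but does not schedule one.

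**Step 5: count again with the adolescent as respondent at the first two assessments.** Parent-completed primary measures become 5 − 1 = 4 of 5. The adolescent takes the test at 2 of 3 assessments, which are the two that define the pre/post endpoint.

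**The case against.** The strongest reply is that this is loose drafting. One combined list covers five instruments, and the later text refers to them only collectively. The team includes PEERS-certified clinicians (Section 2.0), who may know the instrument and give it to the adolescent anyway. The documents never say for whom the test is designed, and the reference cited for it is unpublished. Section 9.0 says that the consent discussion will distinguish the parent's activities from the child's, and the consent forms, which are not in the text reviewed, could list an adolescent form.

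Much of this stands. The intended respondent is inferred from the test's name, from Section 1.0 and from who receives tDCS. A reader might infer that the sponsor chose a parent respondent on purpose, or that adolescents will certainly go untested. The documents support neither. They do support the narrower statement that the written procedure gives the test to the parent consistently, in table and narrative, and that nothing supplied corrects it.

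A second reply is that a parent's score need not be uninformative. Parents review homework and rejoin the adolescents at the end of each session, so a proxy answer could carry part of any effect. That also stands.

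A third is scale: this is one measure of five, in a study aiming for 10 completers, with descriptive analysis under Section 12.0. That limits the consequence. It does not change what the score would measure, whether it is summarised descriptively or tested as Section 4.0 says.

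**Conclusion.** Wrong as written. The plan assigns a primary measure of adolescent knowledge to the parent at 3 of 3 assessments and to the adolescent at 0 of 3, which leaves 5 of 5 primary efficacy measures parent-completed. These counts come straight from the text. That the adolescent should be the respondent is an inference, and the cause may be a drafting slip.

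A reader might go further and conclude that an active-sham difference would be diluted by some known amount, or lost. The documents do not support that. They give no effect size for this measure, no relation between parent and adolescent scores, and no statement of whether the parent answers as self or proxy. What can be said is that the score would not be a direct test of adolescent knowledge, and that the untrained baseline could not be recovered.

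**What to change.** In Section 10.0 and its schedule table, name the respondent for each of the five measures at each visit, and bring Sections 4.0 and 7.0 into line. Suggested text:

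*The adolescent completes the Test of Adolescent Social Skills Knowledge-Revised at the initial visit, before any PEERS session, and again at the post-intervention visit. The parent completes the other four measures.*

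If a parent version is intended, state whether the parent answers as self or as proxy, and report that score separately from adolescent knowledge. An adolescent form at 14 weeks is optional, because the primary endpoint is pre/post.

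The cost is some adolescent time at two visits already planned. The form's length is not given, but the table allots 30 minutes to all the clinical measures at follow-up, so one form should take less. Room is limited:

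- **Initial visit.** The listed activities total 15 + 5 + 90 + (10 to 15) + 30 + 10 = 160 to 165 minutes. With the 10-minute break this is 170 to 175 of roughly 180, and no time is listed for the pregnancy test.
- **Post-intervention visit.** A 30-minute scan slot, as at baseline, leaves 45 − 30 = 15 minutes. If mock scanner training (10 to 15 minutes) is repeated, 0 to 5 remain. The narrative puts scanning at about 20 minutes, which would leave more.

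The 45-minute visit may therefore need a slightly longer stated length. No new visit is needed.

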5.0 Inclusion and Exclusion Criteria/ Study Population

Inclusion Criteria for Adolescents:

- Participants in this study will be youths aged 14-17 with a documented history of ASD who are enrolling in a PEERS program at MUSC.
- Participants will be screened for eligibility using the ADOS-2, the gold standard instrument for diagnosing ASD. A score falling within the autism spectrum range on the ADOS-2 is required.
- Participants will also be screened for IQ using the K-BIT2, an IQ measure appropriate for children and adolescents. Subjects must score higher than 70 on the K-BIT2.
- Participants must be willing to enroll in PEERS training and to receive brain stimulation prior to being included in this study

Exclusion Criteria for Adolescents:

- Epilepsy, or a seizure in the last year
- Vagal nerve stimulators
- Participants may continue to take prescribed medications during the course of the treatment. However, no dosage or agent changes may be made one month prior to the study or during the study. If a medical or behavioral treatment change must be made during the course of the study, participation will be discontinued.
- Allergy to benzocaine
- Prior brain stimulation (tDCS, TMS, ECT, DBS) intervention
- Inability or unwillingness of subject or legal guardian/representative to give informed consent
- Non-native English speaker
- Metal pins, plates or clips in the body or orthodontics
- Surgical implants such as pacemakers or cochlear implants
- Permanent makeup or tattoos near the face or head
- Metal fragments in the body (from welding, shrapnel, BB guns) or suspect that they have fragments
- Claustrophobia
- Past closed head injury or concussion
- Currently under the influence of alcohol or other recreational drugs
- Smoker
- Cannot understand the fMRI task instructions
- Cannot lay still in the mock scanner for a period of 5 minutes
- Prior PEERS training

Inclusion Criteria for Parents:

- Have a child with Autism Spectrum Disorder and willingness and ability to participate in the weekly PEERS session

Exclusion Criteria for Parents:

- Enrolled in an academic course in which Drs. [name], [name], [name] or [name] are instructors

No individual will be excluded based on race, gender, or ethnicity. The parent can be either male or female.

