This project involves both a medical device intervention (tDCS) and a behavioral intervention (PEERS training). fMRI scanning, while not an intervention, will be conducted prior to and following 14-weeks of weekly tDCS sessions.

For tDCS, safety of the participants will be monitored during and immediately after delivery of tDCS to the scalp. During tDCS stimulation, subjects have the option of wearing a ski cap which may reduce discomfort. They will be introduced to the ski cap during the tDCS acclimation session on the initial visit. Some subjects may opt not to wear the ski cap, but it will not affect tDCS delivery. At the end of the sessions that involved tDCS delivery, subjects will be asked if they felt or feel any sensations on the scalp where the electrode was and responses are recorded by the experimenter. In [name] experience and other reports in the literature, any sensations of pain, tingling, itching, stinging or irritation follow the onset of stimulation for about 30-60 seconds and do not persist longer than that. If subjects report feelings of sensation or pain that are unmanageable, a local analgesic cream (benzocaine) can be used or the level of current can be reduced to help them complete the session. [name] will be present during all experimental sessions when tDCS is delivered and will be able to monitor for any adverse medical effects.

Adverse effects will be defined by painful sensations that are unmanageable and cannot be alleviated using the procedures outlined above or by persistent reports of high levels of pain by a participant. Although we do not expect this to occur, such events will be reported to the IRB.

For PEERS training, which is a behavioral intervention, the risks are minimal, but include potential discomfort in interacting with other individuals. Should this intervention prove to be too distressful for an individual, the individual will have the option to discontinue the study. Distress would be indicated by persistent withdrawal from or refusal to engage in PEERS activity, persistent protesting, crying or agitation during PEERS sessions. [name] and the research assistant will make the decision as to whether an individual is experiencing distress. When these behaviors lead to removal from the study, these will be reported as adverse events to the IRB.

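### Section 10.0 specifies latex-cased scalp electrodes, but Section 5.0 has no latex-allergy exclusion and no alternative electrode is described, so an adolescent with known latex allergy is eligible as written (minor)

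*Combined protocol and SAP*

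**What the plan says.** **Electrode.** Section 10.0 specifies 4x4 cm "sponge electrodes soaked in a sterile solution of 0.9% sodium chloride insulated by a latex casing". This is the only mention of latex in the supplied text.

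**Who wears it and how often.** The electrode sentence names no arm. Section 10.0 also says that sham is achieved by "wiring all group participants to separate computer-controlled tDCS programs", and "In all tDCS conditions, the anode will be placed on the scalp". Stimulation accompanies each of 14 weekly PEERS sessions. At the initial visit there are two further placements: first "the child is introduced to the tDCS electrodes placed on the scalp with no stimulation", then, after scanning, "Electrodes are placed on the scalp again", this time with current raised gradually.

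**Eligibility.** The Section 5.0 exclusions for adolescents cover many conditions, but name one allergy: "Allergy to benzocaine". There is no general clause on allergy to study materials.

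**Screening.** Before any placement there is a telephone screen, then medical and MRI screening at the initial visit, where "the medical history information obtained during the initial telephone interview will be reconfirmed".

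**Response to discomfort.** If sensations are unmanageable, Section 13.0 says that "a local analgesic cream (benzocaine) can be used or the level of current can be reduced". Section 15.0 lists sensations at the electrode site and headache as risks of stimulation. It does not list a reaction to the electrode material.

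**The concern.** A protocol that names a common contact allergen as part of a device placed on the scalp would normally either exclude people known to be allergic to it or provide a substitute. This one does neither in the supplied text. It does treat one contact allergy as a reason for exclusion, that to benzocaine, although the cream is used only if sensations become unmanageable. The electrodes are used at every placement, so silence about their material looks like an oversight.

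At stake is an avoidable exposure of a minor. If a parent reports latex allergy at screening, the written protocol gives staff no ground to exclude the adolescent and no other electrode to use. No endpoint, estimate or test depends on the point.

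**Working it through.** The protocol gives no figure to reproduce. The check compares the device description with each place where a latex allergy could be caught or managed.

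**1. Does any eligibility criterion remove the adolescent?** No. In Section 5.0 the only allergy is to benzocaine, and none of the other exclusions (seizures, implants, metal, medication changes, prior stimulation and so on) would apply because of a latex allergy.

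**2. Is another electrode available?** None is described in Section 10.0, in the safety provisions of Section 13.0 or in the device section, 18.0. The two remedies in Section 13.0, cream or lower current, leave the casing in place.

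**3. Would both arms be exposed?** Probably. All participants are wired up, and the anode position is stated for all conditions. The protocol does not state outright that sham participants wear the same electrodes, so this is an inference.

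**4. How many planned placements?**
- Initial visit: 2 (one without current, one with).
- PEERS sessions: up to 14.
- Total for a completer: 2 + 14 = 16.

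This assumes that the acclimation electrodes are those used in the sessions. It is a count from the schedule and does not measure risk.

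**5. What do the existing safeguards do, and when?**

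| Safeguard | Section | Timing | Settles eligibility or supplies a substitute? |
|---|---|---|---|
| Telephone screen, medical screen, history reconfirmed | 10.0 | Before first placement | May reveal an allergy; no written rule on what follows |
| First placement without current | 10.0 | At first exposure | No |
| Noting irritation, discomfort or attempts to remove leads | 10.0 | During exposure | No |
| Stopping the session if the child keeps protesting or is uncomfortable | 9.0 | During exposure | No |
| Team member present at all sessions with stimulation, able to monitor for medical effects | 13.0 | During exposure | No |
| Scalp sensations asked about at the end of stimulation sessions | 13.0 | After exposure | No |
| Investigator may withdraw a participant whose safety is at risk from stimulation (explained there as persistent or intense pain) | 14.0 | After exposure begins | No |

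Only the first row acts before exposure, and its forms are not supplied. The rest limit the consequences of an exposure but do not prevent the first one.

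**6. Can the chance of harm be calculated?** No. It would need the prevalence of latex allergy in this population, whether the casing touches skin, and whether screening asks about it. The documents give none of these.

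**The case against.** The strongest reply is that harm depends on a premise the protocol does not state. The latex insulates a wet sponge; nothing says that it lies against the skin. Handling a known contact allergy through the medical history, without a listed criterion, is also a defensible drafting choice. The screening forms are not in the supplied text and the consent pages were removed, so a question or a warning may exist. Monitoring at every stimulation session and the withdrawal power are written safeguards. With 17 adolescents, an affected one may never present.

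Most of this stands, and it limits the weight of the point. It does not remove the gap: even if screening reveals the allergy, the eligibility list still admits the adolescent and no substitute is described. A consent warning would not change that.

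Three stronger readings are tempting and are not supported:
- *That screening fails to ask about latex.* The forms are unseen, so this cannot be known.
- *That the reason for excluding benzocaine allergy applies with more force to the casing because it is used more often.* This holds only if the casing touches skin. The cream's contact with the scalp follows from its use; the casing's does not.
- *That each adolescent excluded for latex allergy would cost 1 of the 17.* Section 10.0 describes the 17 as randomized participants, and preliminary eligibility is decided by telephone beforehand. Someone screened out at that stage would not normally be among them, and nothing shows that the recruitment pool would run out.

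**Conclusion.** The gap is real and minor. As written, an adolescent with known latex allergy is eligible, and could have electrodes with a latex casing applied at up to 16 planned placements without a written criterion or alternative to prevent it.

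That the exposure matters rests on one assumption: that the casing can touch the skin. That it concerns both arms rests on the inference that sham participants wear the same electrodes. The probability of harm is unquantified. A reader might infer that the trial is unsafe or that a reaction is likely; the documents support neither, given the screening before placement and the supervision during sessions. The effect on the planned analysis is nil.

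**What to change.** Either of two changes closes the gap.

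1. **Exclusion.** Add latex allergy or sensitivity to the adolescent exclusions in Section 5.0, and a matching question to the telephone and medical screen. Cost: one question and possibly a rare screen failure.
2. **Material.** In Section 10.0, specify a latex-free casing of the same 4x4 cm size for all participants in both arms. Keeping the size and using it for everyone leaves the set-up uniform across active and sham, and no one need be excluded on this ground. Cost: a change of materials. The sponsor would need to confirm that a suitable electrode exists for the device, since the documents do not say.

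Neither changes the planned sample size or the analysis. If screening already covers latex, or the casing cannot touch skin, a sentence in the protocol saying so would settle most of the concern.
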